3.1.3 Pregnancy and Early Postpartum Period

Mother:

- Pregnancy period: Laboratory and clinical assessments during the third trimester (gestational Week 35 [±14 days]) will be performed in accordance with planned prenatal care visits, whenever possible. To reduce the burden of visits on the mothers, results from physical and obstetric examinations, as well as neurological examinations, done as part of routine care may be used. *All* visit samples may be collected by home nurse visit. Women may be given vaccines (e.g., for *Bordetella pertussis*) as part of routine obstetric care (note: live or live-attenuated vaccines are not recommended during ocrelizumab treatment and until B-cells return to normal level). Ocrelizumab must not be administered after the woman is enrolled in the study and until the infant's birth. Should this happen, the woman will be discontinued from the study.
- Early postpartum period: A blood sample will be collected from the mother within 24 hours after delivery for assessment of serum ocrelizumab concentration. Treatment with commercial ocrelizumab may be resumed at any time after birth for women who decide not to breastfeed. Some women may decide to resume treatment with ocrelizumab whilst breastfeeding. For those women, treatment with ocrelizumab should be restarted after collection of the infant blood sample at Week 6 of life (±7 days) if possible, but the decision is left to the discretion of the woman and the investigator. If the woman switches to another DMT postpartum, the infant blood sample at Week 6 of life (±7 days) will only be collected if the woman is not breastfeeding.

Infant:

At birth, a blood sample will be collected from the umbilical cord (only for live births; no collection should occur in the event of a pregnancy interruption [i.e., therapeutic abortion

or stillbirth]). The target time frame for collection will be within 1 hour after delivery; the actual time of collection after delivery will be recorded. At Week 6 (\pm 7 days) of the infant's life, a blood sample will be collected from the infant (at an on-site visit, or by home nurse visit) for measurement of B-cell levels (the primary endpoint). For preterm infants, blood samples will be collected at the week of life equivalent to term infants (e.g., if birth occurred at gestational Week 35, blood sample would be collected at Week 8 of life).

Note: If the infant's B-cell levels are found to be below lower limit of normal (LLN), repeat analyses may be done at unscheduled visits at the discretion of the investigator (in consultation with the Sponsor).

3.1.4 Vaccination Period

Both the mother and the infant will enter an extension phase, which will continue approximately until the infant reaches 13 months of age. This is designed to evaluate whether infants potentially exposed to ocrelizumab during pregnancy are able to mount humoral immune responses to clinically relevant vaccines.

Infant laboratory assessments will be performed 1 month (+30 days) after the first dose of MMR vaccine (if first dose is administered at 11 months of age or later) or 1 month (+30 days) after second dose of MMR vaccine (if first dose is administered before 11 months of age), or at Month 13 of chronological age (+30 days), if MMR vaccine is not planned to be administered (as per local clinical practice, vaccinations may include diphtheria, tetanus, pertussis, Hemophilus influenzae type b [Hib], 13-valent pneumococcal conjugate vaccine [PCV-13], hepatitis B virus [HBV], and MMR). Additionally, infants will continue to be followed up for growth (age-adjusted body length, weight and head circumference) and developmental milestones up to 12 months of age. Growth charts following the World Health Organization (WHO) Child Growth Standards (WHO 2022), absolute values and the Ages and Stages Questionnaire, version 3 (ASQ-3) will be used; other standard measurements recorded by e.g., the pediatrician as part of routine postnatal care may also be used. The time windows for infant growth velocity and child developmental milestone assessments are given in Appendix 6. Post-natal timings of ocrelizumab infusions every 6 months and laboratory/clinical assessments in the mother may occur at different time points than infant assessments. In case the mother decides to switch to another DMT or to stop DMT after birth, no laboratory/clinical assessments will be performed for the mother. However, the infant blood sample 1 month (+30 days) after the first or second dose of MMR vaccine (or at Month 13 of age [+30 days]) will still be collected.

A structured telephone interview will be conducted by site personnel postpartum every 3 months (in-between ocrelizumab infusions) for a general review, and to identify and collect information on any changes in the woman's or infant's health status (including the occurrence of MS relapses in the woman and use of new concomitant medications) and possible adverse events in both the woman and the infant (particularly infections);

Ocrelizumab—F. Hoffmann-La Roche Ltd 34/Protocol MN42988, Version 3 women will also be asked if the ASQ-3 form is being filled out. No telephone contact is needed in weeks where the woman is performing on-site visits.

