1.3 STUDY RATIONALE AND BENEFIT-RISK ASSESSMENT

Most patients with MS are women in their reproductive years (Albor et al. 2017; Trojano et al. 2012). Family planning is therefore an important consideration for women with MS who are receiving treatment with DMTs. Women are usually advised to discuss treatment options with their healthcare professional (HCP) prior to family planning, and in many instances, it may be recommended, or even required, that a woman discontinue her treatment with DMTs during pregnancy planning or once pregnancy is confirmed (Hellwig et al. 2020). However, this may lead to an increased risk of relapses during the period between DMT discontinuation and the start of the potential protective effects of pregnancy (Confavreux et al. 1998). For example, severe rebound relapses during pregnancy have been reported as early as 1 month after stopping fingolimod and 3–4 months after stopping natalizumab (Langer–Gould et al. 2019). In addition, there is evidence that approximately 30% of women with MS experience a relapse in the first 3 months after delivery (Vukusic et al. 2004).

Ocrelizumab may be a suitable treatment option for women with MS planning to become pregnant because of its prolonged immunomodulatory effects. The terminal half-life of ocrelizumab (26 days on average) provides a window of opportunity for a woman to become pregnant when B-cells remain undetectable despite the medication already being cleared from the body, or not being able to cross the placental barrier. Currently, the ocrelizumab labeling (Summary of Product Characteristics [SmPC], U.S. Prescribing Information [USPI]) stipulates that contraceptives should be used during ocrelizumab treatment, and for 6 months (United States) or 12 months (EU) after the last dose.

Ocrelizumab—F. Hoffmann-La Roche Ltd

The 6-month contraceptive requirement in the US label reflects the pharmacokinetic properties of ocrelizumab, including the lack of transfer across the placenta during the first trimester of pregnancy owing to its conformation as an IgG1 antibody (Kane and Acquah 2009).

Available Evidence

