	• Note: Immune responses to the following may be included: measles, mumps, rubella, tetanus , diphtheria, pertussis, varicella zoster, Streptococcus pneumoniae , HBV, and SARS-CoV-2; along with nucleocapsid and spike protein titers; only for those mothers who have received the vaccine, as per local clinical practice)
 To measure disease activity in mothers during pregnancy and postpartum 	 Number of MS relapses during pregnancy and postpartum (clinical relapses)
	 Mean change from baseline in the EDSS score over the course of the study
 To detect presence of neuroaxonal damage in the mother during pregnancy and postpartum 	• sNfL levels during pregnancy (second trimester [time frame of blood sampling: Week 24–30], third trimester [time frame of blood sampling: Week 35] and at delivery [time frame of blood sampling: within 24 hours after delivery]) and postpartum (in line with ocrelizumab administration timepoints)

Table 1 Objectives and Corresponding Endpoints (cont.)

ASQ-3 = Ages and Stages Questionnaire, version 3; EDSS = Expanded Disability Status Scale; HBV = hepatitis B virus; Hib = Hemophilus influenzae type b; LLN = lower limit of normal; MMR = measles, mumps, and rubella; MS = multiple sclerosis; PCV-13 = 13-pneumococcal conjugate vaccine; SARS-CoV-2 = severe acute respiratory syndrome coronavirus 2; sNfl = serum neurofilament light chain; WHO = World Health Organization.

Table 1 Objectives and Corresponding Endpoints (cont.)

Objectives	Corresponding Endpoints
Exploratory Objectives (cont.)	
 To evaluate the evolution of B-cell levels between birth and the first year of life 	 Trajectory (absolute and percentage changes) of B-cell (CD19 + cell) levels in the infant from Week 6 of life to 1 month after the first or second dose of MMR vaccine or Month 13 of age in case MMR vaccine is not planned to be administered

ASQ-3=Ages and Stages Questionnaire, version 3; EDSS=Expanded Disability Status Scale; HBV=hepatitis B virus; Hib=Hemophilus influenzae type b; LLN=lower limit of normal; MMR=measles, mumps, and rubella; MS=multiple sclerosis; PCV-13=13-pneumococcal conjugate vaccine; SARS-CoV-2=severe acute respiratory syndrome coronavirus 2; sNfl=serum neurofilament light chain; WHO=World Health Organization.

3. STUDY DESIGN

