4.5.2.5 Assessment of Relapses

Potential relapses should be recorded throughout the study period after screening. See Appendix 1 (Schedule of Assessments) for the timing of these assessments.

All new or worsening neurological events consistent with MS representing a "clinical relapse" are to be reported on the dedicated "MS relapse" form. A clinical relapse is defined as a monophasic clinical episode with patient-reported symptoms and objective findings typical of MS, reflecting a focal or multifocal inflammatory demyelinating event in the CNS, developing acutely or sub-acutely, with a duration of at least 24 h, with or without recovery, and in the absence of fever or infection (Thompson et al. 2018). Multiple sclerosis relapses should not be reported as an AE, unless they are serious.

It is recommended that women with new neurological symptoms suggestive of a relapse have an EDSS/Functional Systems Scores (FSS) assessment performed as soon as possible, ideally within 7 days of the onset of symptoms. However, it is not mandatory to perform an EDSS assessment in case of a suspected relapse.

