4.5.2.6 Assessment of Disability

Disability in MS will be measured by the EDSS. See Appendix 1 (Schedule of Assessments) for the timing of assessments.

The EDSS is based on a standard neurological examination, incorporating seven functional systems (pyramidal, cerebellar, brainstem, sensory, bowel and bladder, visual, and cerebral [or mental], plus "other") rated and scored as FSSs. Each FSS is an ordinal clinical rating scale ranging from 0 to 5 or 6. These ratings are then used in conjunction with observations and information concerning ambulation and use of assistive devices to determine the EDSS score. The EDSS is a disability scale that ranges in 0.5-point steps from 0 (normal) to 10 (death) (see Appendix 4). *The EDSS*

assessment may also be performed by the investigator via telephone, using a specific licensed questionnaire (see Appendix A4–2).

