6.1 DETERMINATION OF SAMPLE SIZE

The study will include approximately 33 pregnant women.

There is no formal sample size calculation, as no confirmatory hypothesis testing is planned. The primary analysis will be descriptive. Considering a 10% dropout rate, *approximately 30* evaluable infants are expected. A further investigation will be performed on the subgroup of infants whose mothers received the last dose of ocrelizumab 0–3 months before the LMP or during the first trimester.

The precisions (width of the two-sided 95% CIs based on normal approximation) for different event rates (an "event" is defined as B-cell levels below LLN) are shown in the following table. If no event is observed from the 30 infants during the study, there is a 95% confidence that the event rate is below 0.114.

Sample Size	Number of Events	Event Rate	Precision
30	1	0.033	0.165
30	2	0.067	0.195
30	3	0.100	0.222
30	4	0.133	0.244
30	5	0.167	0.262

Table 5 Precision at Different Event Rates

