2.2 DETERMINATION OF SAMPLE SIZE

The study will include approximately 33 pregnant women.

There is no formal sample size calculation, as no confirmatory hypothesis testing is planned. The primary analysis will be descriptive. Considering a 10% dropout rate, approximately 30 evaluable infants are expected. A further investigation will be performed on the subgroup of infants whose mothers received the last dose of ocrelizumab 0-3 months before the LMP or during the first trimester

The precisions (width of the two-sided 95% confidence intervals [CIs] based on normal approximation) for different event rates (an "event" is defined as B-cell levels below lower limit of normal [LLN]) are shown in the following table. If no event is observed from the 30 infants during the study, there is a 95% confidence that the event rate is below 0.114.

Sample Size	Number of Events	Event Rate	Precision
30	1	0.033	0.165
30	2	0.067	0.195
30	3	0.100	0.222
30	4	0.133	0.244
30	5	0.167	0.262

 Table 1
 Sample Size Precision at Different Event Rates

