4.6.2 Infants Childhood Developmental Milestones

The infant's developmental milestones will be assessed using the Ages and Stages Questionnaire version 3 (ASQ-3), in the domains of communication, gross motor, fine motor, problem solving, and personal-social at Week 6 and Months 2, 4, 6, 9, and 12.

The total score for each domain will be summarized by visit using continuous statistics in the SAFI. In addition, the number and percentage of infants with abnormal scores (Yes/No) will be presented in the SAFI, as per cut-offs below transcribed from the ASQ-3 User's guide.

450.2	Area				
questionnaire	Communication	Gross Motor	Fine Motor	Problem Solving	Personal Social
Month 2	22.77	41.84	30.16	24.62	33.71
Month 4	34.60	38.41	29.62	34.98	33.16
Month 6	29.65	22.25	25.14	27.72	25.34
Month 9	13.97	17.82	31.32	28.72	18.91
Month 12	15.64	21.49	34.50	27.32	21.73

ASQ-3=Ages and Stages Questionnaire version 3.

Values below the respective cut-off will be classified as abnormal (i.e., further assessment with a professional may be needed).

A corresponding listing will be produced.

Only questionnaires assigned to the correct time point will be included in the main analysis. If the wrong questionnaire is used for some time points in >20% infants, a sensitivity analysis will be performed with these data included.

4.6.3 Women's Immunity During Pregnancy

To evaluate humoral immunity to clinically relevant pathogens in mothers during pregnancy. Serum antibody (IgG) titers to immunizations: for measles, mumps, rubella, TT, diphtheria, pertussis, varicella zoster, Streptococcus pneumoniae, HBV and SARS-CoV-2 (along with nucleocapsid and spike protein titers; only for those mothers who have received the vaccine, as per local clinical practice) will be collected in the third trimester (Week 35). This will be presented in the same way as for infant immune response in Section 4.5.3 but for the SAFW population.

A listing with all immune response will be produce.

4.6.4 Women's Disease Activity

To assess disease activity and progression in women, the potential relapse is recorded and EDSS, a neurological examination is performed during pregnancy (Week 24-30 and Week 35), at infusion (if applicable), at early discontinuation and unscheduled visit if applicable. This will be summarized as follows in the FASW:

- Clinical Relapse:

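### Scheduled postpartum EDSS and sNfL exist only at ocrelizumab infusions, yet the SAP pools postpartum disease activity over all women with no split by postpartum treatment

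*Protocol*

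**What the plan says.** Protocol Section 2 (Table 1) sets an exploratory objective for all mothers: "To measure disease activity in mothers during pregnancy and postpartum". Its endpoints are the number of relapses and the mean change in EDSS. Postpartum sNfL belongs to a separate exploratory objective, neuroaxonal damage, and that endpoint is itself tied to ocrelizumab administration times.

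In the schedule of assessments (protocol Appendix 1), maternal EDSS, neurological examination and relapse recording after delivery are marked at Visit 5 (Infusion 1), Visit 6 (Infusion 2) and the woman's early-discontinuation visit. After the delivery sample, sNfL is marked only at Visits 5 and 6. A footnote links those two visits to the mother's infusions, and Infusion 1 has no fixed date. Protocol 3.1.4 states that if the mother decides "to switch to another DMT or to stop DMT after birth, no laboratory/clinical assessments will be performed for the mother"; infant sampling continues.

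Other passages widen what is collected. Protocol 3.1.4 has site staff ask every mother about relapses by telephone every 3 months. Protocol 4.5.2.5 records relapses throughout the study. Protocol 4.5.2.4 asks for a prompt neurological evaluation of new or worsening symptoms at any point. SAP 4.6.4 places the postpartum assessments "at infusion (if applicable), at early discontinuation and unscheduled visit if applicable".

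SAP 4.6.4 then summarises, in the FASW, mean EDSS by 3-month interval including after pregnancy, EDSS change by visit, and relapses to 1 year after delivery, with an optional annualised rate. Its only subgroups are by ocrelizumab exposure before the study. SAP 4.6.5 gives no split for sNfL.

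**The concern.** Whether a woman has a scheduled postpartum EDSS or sNfL, and when, depends on whether and when she restarts ocrelizumab. A mean taken over the women who were assessed, but labelled as an FASW result, invites the reader to take it as the course of the whole cohort after pregnancy. It is the course of a group selected by treatment.

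Relapses raise a different problem. All women stay in the summary, but how a relapse is found differs. Women who restart have scheduled examinations at infusions. The others have a telephone call and whatever examination follows from it. The definition in protocol 4.5.2.5 requires "patient-reported symptoms and objective findings typical of MS", which a call alone does not supply. One pooled count or rate therefore combines time on and off ocrelizumab with unequal ascertainment.

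**Working it through.** **Inputs from the documents**

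- Cohort size (protocol 6.1): "The study will include approximately 33 pregnant women".
- Expected attrition (SAP 2.2): "Considering a 10% dropout rate, approximately 30 evaluable infants are expected". Check: 33 × (1 − 0.10) = 29.7, about 30. The plan's figure is reproduced.
- Early postpartum relapse risk cited in protocol 1.3: "approximately 30% of women with MS experience a relapse in the first 3 months after delivery".
- Fraction of women restarting ocrelizumab: not given. It is taken below as an assumption, from 90% down to 30%.

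**Who has scheduled postpartum data**

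| Source | Restarts ocrelizumab | Switches or stops DMT |
|---|---|---|
| EDSS and examination at Visits 5 and 6 | yes, dated by infusion | none |
| sNfL at Visits 5 and 6 | yes, dated by infusion | none |
| 3-monthly telephone question on relapses | yes | yes |
| Examination for new symptoms, unscheduled | possible | possible, but in conflict with protocol 3.1.4 |
| EDSS at early discontinuation | if she leaves | if she leaves |

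For a woman who stays in the study and does not restart, nothing scheduled supplies EDSS or sNfL after delivery.

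**Effect on a pooled mean**

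Let f be the fraction who restart, m_R the mean in women who restart and m_N the mean in those who do not. If only restarters are observed:

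observed mean − all-women mean = m_R − [f·m_R + (1 − f)·m_N] = (1 − f)·(m_R − m_N)

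With 33 women and whole-number counts:

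| Assumed restart | Restart | No scheduled EDSS or sNfL | Error as a multiple of (m_R − m_N) |
|---|---|---|---|
| 90% | 30 | 3 | 3/33 = 0.09 |
| 70% | 23 | 10 | 10/33 = 0.30 |
| 50% | 16 | 17 | 17/33 = 0.52 |
| 30% | 10 | 23 | 23/33 = 0.70 |

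With 30 women, the numbers without scheduled data are 3, 9, 15 and 21. The documents give no value for m_R − m_N, so only the multiplier can be stated.

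**Timing**

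If the cited 30% applied here, 33 × 0.30 = 9.9, so about 10 women would relapse within 3 months of delivery. Infusion 1 can fall at any time after birth, so some of these relapses can precede a woman's first scheduled postpartum EDSS even if she restarts later.

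**What the SAP does elsewhere**

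SAP 4.5.3 splits infant titres by whether the mother received postpartum ocrelizumab. SAP 4.8.2 separates maternal adverse events before and after the first postpartum infusion. SAP 4.8.1 tabulates postpartum DMT type and time to the first postpartum dose. SAP 4.6.4 and 4.6.5 use none of these splits.

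**The case against.** The best defence is that much of this is disclosed or can be recovered. The sNfL endpoint states its own timing. EDSS change is reported by visit, and the postpartum visits are the infusions. Summaries show n, and SAP 4.8.1 lets a reader count the women who restarted. The annualised rate is optional. All these endpoints are exploratory and descriptive, and splitting about 33 women gives small cells. A woman who only delays ocrelizumab, for example while breastfeeding, is still assessed at Infusion 1.

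These points stand, and they limit the weight of the concern. They do not cover mean EDSS by 3-month interval, where the link to an infusion visit disappears from the table, or the pooled relapse summary, where n does not reveal how relapses were ascertained.

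The defence is also right about relapse capture. A reader might infer that the disease-activity objective is answered only for women who restart. The documents do not support that: relapses are recorded throughout the study and asked about by telephone for all mothers. Nor does a relapse first reported by telephone necessarily fail the definition. Protocol 4.5.2.4 asks for a prompt evaluation and allows a referred woman's routine neurology results to be used.

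**Conclusion.** The point holds for scheduled EDSS and sNfL, and for the way SAP 4.6.4 pools results. Postpartum EDSS describes mainly women who restarted ocrelizumab, at dates set by their restart. Relapses cover all women, but with unequal ascertainment and no separation by postpartum treatment.

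The size rests on an assumed restart fraction. From 90% to 30% restarting, 3 to 23 of 33 women lack scheduled data, and the error in a pooled mean is 0.09 to 0.70 times an unknown group difference. If the two groups do not differ, there is no error.

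A reader might also apply the 30% relapse risk to the women who do not restart and conclude that a given share of relapses goes unconfirmed. That share would only return the assumed non-restart fraction. It would also treat every such relapse as unexamined, which protocol 4.5.2.4 contradicts. No such estimate is supported.

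Separately, the absence of maternal assessments in protocol 3.1.4 conflicts with the prompt evaluation in 4.5.2.4 and the unscheduled visits in SAP 4.6.4. The primary endpoint and the sample size are unaffected. This is an inexpensive improvement to exploratory reporting.

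**What to change.** 1. In SAP 4.6.4 and 4.6.5, present postpartum EDSS, sNfL and relapses by postpartum ocrelizumab status, using the with/without split of SAP 4.5.3. Label scheduled postpartum EDSS and sNfL as data from women who restarted ocrelizumab, and show how many FASW women were not assessed.
2. If an annualised postpartum relapse rate is presented, compute it with person-time before and after the first postpartum ocrelizumab dose, the same cut point that SAP 4.8.2 uses for maternal adverse events. Women who never restart contribute only to the first period. List relapses known by telephone only separately from examined ones.
3. Reconcile protocol 3.1.4 with protocol 4.5.2.4 and SAP 4.6.4 on whether women who switch or stop DMT can be examined.

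Items 1 and 2 are SAP wording. Postpartum DMT and dose dates are already collected. The documents do not show whether the relapse form records how a relapse was ascertained; if it does not, relapse dates can be matched to examination dates. The cost is small cells, so these tables should be read as descriptive. Item 3 is a clarification of text.

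An added telephone EDSS schedule is not proposed. Protocol 4.5.2.6 says the EDSS "assessment may also be performed by the investigator via telephone", but Appendix A4-2 intends that form for patients who exceptionally cannot attend. A new schedule would also contradict protocol 3.1.4 and need an amendment.
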